5. STUDY DESIGN

5.1 Overall Design

Table 5.2.1 details assessments for Phase 1 Cohort 1, and Table 5.2.2 for Phase 1 Cohort 2. Every effort must be made to follow the schedule of assessments within the windows outlined in the protocol.

- For the first 6 weeks, all assessments have a \pm 3 day window unless otherwise indicated.
- After the first 6 weeks, all assessments have a \pm 7 day window, unless otherwise indicated. Additional assessment may be performed as clinically indicated.

If study drug is being held due to toxicity, then the scheduled visits and assessments should still be performed per protocol (except dose administration), unless otherwise specified.

Table 5.2.2: Phase I Cohort 1															
Trial Period:		Screen Phase	Treatment										End of Treatment	Post-Treatment	
Treatment Cycle/Title:		Screen	D1 W1	D1 W2	D1 W3	D1 W4	D1 W5	D1 W6	D1 W7	D1 W8	D1 W9	D1W 14 (+)	Discon	Safety Follow-up	Follow Up Visits
Scheduling Window (Days):	28 days	± 3	± 3	± 3	± 3	± 3	± 3	± 3	± 3	± 3	± 3	At time of Discon	100 days post discon	Every 12 weeks post discon	
Informed Consent	X														
Inclusion/Exclusion Criteria	X														
Demographics and Medical History	X														
Prior and Concomitant Medication Review	X	X			X			X			X	X			
Trial Treatment Administration ^a		X			X			X			X	X			
Review Adverse Events	X	X			X			X			X	X			
Nursing Call Check-Up			X	X		X	X		X	X		X			
Physical Examination	X	X			X			X			X	X	X	X	X
Vital Signs	X	X			X			X			X	X	X	X	X
ECOG Performance Status	X	X			X			X			X	X	X	X	X
Pregnancy Test	X														
EKG	X														
CBC with Differential	X	X	X	X	X			X			X	X	X	X	X
Comprehensive Serum Chemistry Panel	X	X	X	X	X			X			X	X	X	X	X
HCV, HIV, HepB	X														
TSH (T3, FT4 if TSH abnormal)	X	X	X	X	X			X			X	X	X	X	X
Research blood collection ^b	X				X								X		
Archival tumor collection	X														
Fresh tumor biopsy ^c	X				X ^c										
Imaging ^d	X														

- a. Encorafenib and binimetonib are given continuously. Nivolumab and ipilimumab are given for four doses every 3 weeks then nivolumab is given monthly for up to one year.
- b. Blood will be drawn at baseline, week 4, week 12 (or with first restaging imaging) and at progression/end of treatment
- c. Ten patients in each Phase Ib cohort will undergo fresh biopsy prior to treatment and between the 1st and 2nd doses of ipilimumab (between weeks 4-7). These will be the first 10 unless medical or societal factors (e.g. COVID19) limit the pursuit of research biopsies.
- d. During treatment: Every 12 weeks (± 7 days). End of Treatment (EOT): if a scan was not conducted within 30 days prior to end of study treatment. Efficacy follow-up: Every 12 weeks starting from the last assessment until documented disease progression per RECIST 1.1 (unless meeting criteria for treatment beyond progression), withdrawal of consent, lost to follow-up, or death irrespective of start of new anti-neoplastic therapy.

e. Table 5.2.2: Phase I Cohort 2																
Trial Period:		Screen Phase	Treatment										End of Treatment	Post-Treatment		
Treatment Cycle/Title:		Screen	D1 W1	D1 W2	D1 W3	D1 W4	D1 W5	D1 W6	D1 W7	D1 W8	D1 W9	D1W 10	D1W 14 (+)	Discon	Safety Follow-up	Follow Up Visits
Scheduling Window (Days):	28 days	± 3	± 3	± 3	± 3	± 3	± 3	± 3	± 3	± 3	± 3	± 3	± 3	At time of Discon	100 days post discon	Every 12 weeks post discon
Informed Consent	X															
Inclusion/Exclusion Criteria	X															
Demographics and Medical History	X															
Prior and Concomitant Medication Review	X	X			X			X			X	X				
Trial Treatment Administration ^a		X			X			X			X	X				
Review Adverse Events	X	X			X			X			X	X				
Nursing Call Check-Up			X	X		X	X		X	X		X				
Physical Examination	X	X			X			X			X	X		X		X
Vital Signs	X	X			X			X			X	X		X		X
ECOG Performance Status	X	X			X			X			X	X		X		X
Pregnancy Test	X															
EKG	X															
CBC with Differential	X	X	X	X	X			X			X	X		X		X
Comprehensive Serum Chemistry Panel	X	X	X	X	X			X			X	X		X		X
HCV, HIV, HepB	X															
TSH (T3, FT4 if TSH abnormal)	X	X	X	X	X			X			X	X		X		X
Research blood collection ^b	X				X									X		
Archival tumor collection	X															
Fresh tumor biopsy ^c	X				X ^c											
Imaging ^d	X															

- a. Encorafenib and binimeteinib are given continuously. Nivolumab and ipilimumab are given for four doses every 3 weeks then nivolumab is given monthly for up to one year.
- b. Blood will be drawn at baseline, week 4, week 12 (or with first restaging imaging) and at progression/end of treatment
- c. Ten patients in each Phase Ib cohort will undergo fresh biopsy prior to treatment and between the 1st and 2nd doses of ipilimumab (between weeks 4-7). These will be the first 10 unless medical or societal factors (e.g. COVID19) limit the pursuit of research biopsies.
- d. During treatment: Every 12 weeks (± 7 days). End of Treatment (EOT): if a scan was not conducted within 30 days prior to end of study treatment. Efficacy follow-up: Every 12 weeks starting from the last assessment until documented disease progression per RECIST 1.1 (unless meeting criteria for treatment beyond progression), withdrawal of consent, lost to follow-up, or death irrespective of start of new anti-neoplastic therapy.

5.1.1 Retesting During Screening or Lead-in Period

Retesting of laboratory parameters and/or other assessments during the Screening or Lead-in period will not be permitted (this does not include parameters that require a confirmatory result) unless there was a technical error in performance of the lab test and the first result is invalid.

Any new result will override the previous result (ie, the most current result prior to dosing) and is the value by which study inclusion will be assessed, as it represents the subject's most current, clinical state.

5.2 Safety Assessments

5.2.1 Medical History, Physical Exam, Physical Measurements

At baseline, a medical history will be obtained to capture relevant underlying conditions. The baseline examinations should include weight, height, ECOG Performance Status, blood pressure (BP), heart rate (HR), temperature, and oxygen saturation by pulse oximetry at rest (also monitor amount of supplemental oxygen if applicable) should be performed within 28 days prior to first dose.

Baseline local laboratory assessments should be done within 14 day prior to first dose and are to include: CBC w/differential, Chemistry panel including: LDH, AST, ALT, ALP, T.Bili, BUN or serum urea level, creatinine, Ca, Mg, Na, K, Cl, Glucose, amylase, lipase, TSH, Free T4, Free T3, Hep B/C (HBV sAG, HCV antibody, or HCV RNA).

While on-study and during follow-up, local laboratory assessments are to be conducted as specified below.

Participants will be evaluated for safety if they have received any study drug. Toxicity assessments will be continuous during the treatment phase. Once participants reach the survival follow-up, either in-person visits or documented telephone calls/email correspondence to assess the subject's status are acceptable.

AEs and laboratory values will be graded according to the NCI-CTCAE version 5.0. Oxygen saturation by pulse oximetry at rest (also monitor amount of supplemental oxygen if applicable) should be assessed at each on-study visit prior to dosing. The start and stop time of the study therapy infusions should be documented.

Physical examinations are to be performed as specified in Section 5.1 and as clinically indicated. If there are any new or worsening clinically significant changes since the last exam, report changes on the appropriate non-serious or serious AE page.

On treatment local laboratory assessments are to be completed within 72 hours prior to dosing.

Additional measures, including non-study required laboratory tests, should be performed as clinically indicated or to comply with local regulations. Laboratory toxicities (eg, suspected drug induced liver enzyme evaluations) will be monitored during the follow-up

Phase I/II study of encorafenib and binimetinib with nivolumab and low dose ipilimumab in metastatic *BRAF* mutant melanoma

phase via on site/local labs until all study drug related toxicities resolve, return to baseline, or are deemed irreversible.

If a subject shows changes on pulse oximetry or other pulmonary-related signs (hypoxia, fever) or symptoms (eg. dyspnea, cough, fever) consistent with possible pulmonary-related signs (hypoxia, fever) or symptoms (eg, dyspnea, cough, fever) consistent with possible pulmonary AEs, the subject should be immediately evaluated to rule out pulmonary toxicity, according to the suspected pulmonary toxicity management algorithm.

Some of the assessments referred to in this section may not be captured as data in the eCRF. They are intended to be used as safety monitoring by the treating physician. Additional testing or assessments may be performed as clinically necessary or where required by institutional or local regulations.

5.2.2 Vital Signs

Vital signs consist of blood pressure, heart rate, respiratory rate, pulse oximetry and temperature measurements. Vital signs will be obtained as outlined above.

5.2.3 Imaging Assessment for Study

CT and MRI scans (section 5.4) will be assessed locally per the modified RECIST 1.1 criteria and RANO BM criteria ^{69,70}. Up to 5 extracranial and 5 intracranial lesions will be followed for efficacy per the criteria. Please refer to Appendix 1 and 5 for guidelines regarding images, target lesion selection and response criteria.

Any incidental findings of potential clinical relevance that are not directly associated with the objectives of the protocol should be evaluated and handled by the Study Investigator as per standard medical/clinical judgment.

Clinically significant radiologic findings or changes from baseline scans will be coded as AEs or serious AEs according to the criteria described in Section6.

5.2.4 ECOG Status

ECOG performance status will be evaluated at the screening evaluation and at each visit as outlined.

5.2.5 AE Monitoring

AEs will be evaluated according to the NCI CTCAE Version 5.0 on a continuous basis starting from when the subject takes the first dose of study administration, up to and including Follow-Up and End of Treatment visits (at minimum, for 100 days following last dose of study drug). Serious AEs (SAEs) must be collected from the time period following p first dose of study drug to and including follow-up (refer to section 5.4).

5.2.6 Laboratory Test Assessments

Results of all safety laboratory collections must be obtained and reviewed in advance of study drug dosing, as applicable. Amylase and lipase should be collected with the chemistry collection, but these lab results do not require review prior to dosing.

Serum Chemistry includes comprehensive metabolic panel (albumin, blood urea nitrogen, calcium, carbon dioxide, chloride, creatinine, glucose, potassium, sodium, total bilirubin and protein, alanine aminotransferase, alkaline phosphatase, and aspartate aminotransferase) with magnesium, phosphorous, amylase, lipase, lactate dehydrogenase. A free-T4 and free-T3 will be performed reflexively for out of range TSH values. A CBC with differential is to be obtained. The CBC with differential includes hemoglobin, hematocrit, white blood cells, platelets (direct platelet count), erythrocyte sedimentation rate, WBC differential enumeration of total and percentage of neutrophils, lymphocytes, eosinophils, basophils and monocytes.

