4.7 DLT

DLT-evaluable participants will be defined as participants who in the DLT evaluation period received $\geq 66\%$ of encorafenib and/or binimetonib doses and at least one dose each of nivolumab and ipilimumab.

For Cohort 1, encorafenib and nivolumab and ipilimumab will be administered on day 1 week 1. The DLT evaluation period will extend from day 1 of week 1 to the end of week 6 and captured in the medical records.

For Cohort 2, encorafenib, binimetonib, nivolumab and ipilimumab will be administered on day 1 week 1. The DLT evaluation period will extend from day 1 week 1 to the end of week 6 and captured in the medical records.

DLT Definition: A DLT is defined as any AE or laboratory abnormality that is not explained by underlying disease, disease progression, intercurrent illness, or concomitant therapies that either meets the criteria described below or results in the inability to tolerate at least 66% of the planned dose of encorafenib +/- binimetonib and at least one dose each of nivolumab and ipilimumab during Cycle 1. CTCAEv5 will be used for grading.

Dose delay criteria apply for all drug-related AEs (regardless of whether or not the event is attributed to nivolumab, ipilimumab, encorafenib, or binimetonib. If investigator can

Phase I/II study of encorafenib and binimetinib with nivolumab and low dose ipilimumab in metastatic *BRAF* mutant melanoma

attribute AE to either targeted or immunotherapy, may hold one and continue the other, otherwise delaying all study drugs is appropriate.

Specific DLT Criteria

Hematologic

- Grade 4 anemia
- Grade 4 neutropenia (for > 7 consecutive days) or Grade 4 febrile neutropenia
- Grade 4 thrombocytopenia (of any duration).
- Grade 3 thrombocytopenia with clinically significant bleeding regardless of duration or requirement of platelet transfusion

Pancreas

- Symptomatic serum amylase or lipase elevation, medical intervention required (pancreatitis Grade 3 or higher)

Gastrointestinal disorders

- Nausea and vomiting \geq Grade 3 for > 3 days despite optimal anti-emetic therapy
- \geq Grade 3 diarrhea for > 5 days despite optimal antidiarrheal treatment (which could include steroids).

Hepatobiliary

- Total bilirubin Grade \geq 4
- For participants with normal baseline AST and ALT values
 - AST or ALT >8 x ULN
- For participants with normal baseline AST and ALT and normal baseline bilirubin value:

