Grade 3	Interrupt dosing of encorafenib and binimetinib and refer patient to ophthalmologist within 7 days. 
 • If resolved to Grade ≤ 1 in ≤ 21 days, resume treatment at 1 reduced dose level of encorafenib and binimetinib. • If not resolved to Grade ≤ 1 in ≤ 21 days, permanently discontinue encorafenib and binimetinib and close follow-up with ophthalmic monitoring until stabilization or resolution
Grade 4	Permanently discontinue encorafenib and binimetinib and immediate follow-up with ophthalmic monitoring until stabilization or resolution.
Interstitial Lung Disease	
Grade 2	Withhold binimetinib for up to 4 weeks. 
 • If improved to Grade 0–1, resume at a reduced dose. • If not resolved within 4 weeks, permanently discontinue
Grade 3 or Grade 4	Permanently discontinue
Rhabdomyolysis or Creatine Phosphokinase (CPK) elevations	
Grade 4 asymptomatic CPK elevation or Any Grade CPK elevation with symptoms or with renal impairment	Withhold binimetinib dose for up to 4 weeks. 
 • If improved to Grade 0–1 resume at a reduced dose. • If not resolved within 4 weeks, permanently discontinue binimetinib

Severity of Adverse Event	Dose Modification
Dermatologic	
Grade 2	If no improvement within 2 weeks, withhold until Grade 0–1. Resume at same dose if first occurrence or reduce dose if recurrent.
Grade 3	Withhold until Grade 0–1. Resume at same dose if first occurrence or reduce dose if recurrent.
Grade 4	Permanently discontinue
Nausea/Vomiting	
Grade 1–2	Maintain dose level of encorafenib and binimatinib. Promptly institute antiemetic measure.
Grade 3	Interrupt dosing of encorafenib and binimatinib until resolved to Grade \leq 1. Then resume treatment at 1 reduced dose level of encorafenib. Resume treatment with binimatinib at the current dose if, in the judgment of the Investigator, the toxicity is considered to be unrelated to binimatinib, or at 1 reduced dose level. Note: Interrupt dosing of encorafenib and binimatinib for \geq Grade 3 vomiting or Grade 3 nausea only if the vomiting or nausea cannot be controlled with optimal antiemetics (as per local practice).
Grade 4	Permanently discontinue encorafenib and binimatinib
Other Adverse Reactions (including hemorrhage)	

Severity of Adverse Event	Dose Modification

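### Binimetinib must be held, then reduced or stopped, for silent Grade 4 CPK, but the plan schedules no CPK test

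*Combined protocol and SAP*

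**What the plan says.** The rule is in Appendix 3, under rhabdomyolysis or CPK elevations. Its trigger is "Grade 4 asymptomatic CPK elevation or Any Grade CPK elevation with symptoms or with renal impairment" and its first action is "Withhold binimetinib dose for up to 4 weeks". Binimetinib restarts at a reduced dose if the event improves to Grade 0–1, and stops permanently if it has not resolved within 4 weeks.

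The laboratory plan is in three places:

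- Section 5.2.1 (baseline) asks for a "Chemistry panel including: LDH, AST, ALT, ALP, T.Bili, BUN or serum urea level, creatinine" and continues through electrolytes, glucose, amylase, lipase, thyroid tests and hepatitis serology. CPK is not listed.
- Section 5.2.6 (serum chemistry) itemises a metabolic panel and five added analytes: "total bilirubin and protein, alanine aminotransferase, alkaline phosphatase, and aspartate aminotransferase) with magnesium, phosphorous, amylase, lipase, lactate dehydrogenase". CPK is not listed.
- The Cohort 1 and Cohort 2 schedules in Section 5.1 have laboratory rows for blood count, "Comprehensive Serum Chemistry Panel", viral serology, TSH and pregnancy test. There is no CPK row.

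On timing, Section 5.2.1 says "On treatment local laboratory assessments are to be completed within 72 hours prior to dosing", and Section 5.2.6 says "Results of all safety laboratory collections must be obtained and reviewed in advance of study drug dosing". Section 5.2.1 also provides for tests outside the study list when clinically indicated.

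**The concern.** Every branch of the Appendix 3 rule needs a CPK value: one to find the event and a later one to judge recovery. Symptomatic cases should come to light clinically and are not at issue. The asymptomatic Grade 4 limb is different, because by definition the patient has no symptom that would lead a clinician to order the test.

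The main stake is patient safety. A patient who meets the plan's own criterion for holding binimetinib could continue it at full dose because nobody looked. The risk is known to the plan: Section 1.1.2.2 lists raised CPK (5%) among the Grade 3 or 4 laboratory abnormalities seen with encorafenib plus binimetinib.

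A secondary stake is the DLT count. Section 4.7 counts other Grade 3 or higher events as DLTs, with limited exceptions, so no change to that definition is needed. A value that was never drawn, however, cannot be counted.

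**Working it through.** The plan states no figure on this point, so there is nothing to reproduce. The core check is textual; the arithmetic only gives scale.

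**Search for CPK.** It appears in the background (Section 1.1.2.2) and in Appendix 3. It is in neither laboratory list and neither Phase I schedule. The rule therefore has no scheduled measurement behind it.

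**Inputs for scale.**

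- Cohort 2 has 12 patients and Phase II up to 60 (Section 8.3). If the quadruplet becomes the recommended regimen, 12 + 60 = 72 patients receive binimetinib.
- The only rate given is 5% Grade 3 or 4 CPK for the doublet over whole treatment. It is neither Grade 4 only, nor a 6-week rate, nor a rate for four drugs, and it does not bound the quadruplet.
- Assumption: a silent, missed-event rate p between 0.5% and 5%.

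**Expected cases and chance of at least one.** Expected = n × p; chance = 1 − (1 − p)^n.

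| p | Expected, n = 12 | At least one, n = 12 | Expected, n = 72 | At least one, n = 72 |
|---|---|---|---|---|
| 0.5% | 0.06 | 5.8% | 0.36 | 30.3% |
| 1% | 0.12 | 11.4% | 0.72 | 51.5% |
| 2% | 0.24 | 21.5% | 1.44 | 76.7% |
| 5% | 0.60 | 46.0% | 3.60 | 97.5% |

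**Illustrative effect on the Cohort 2 DLT count.** Let X ~ Bin(12, r) be the other DLTs and Y | X ~ Bin(12 − X, p) the missed ones, assumed independent, with none detected at present. Three lines matter:

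- 6 to 7 of 12: the exact one-sided 90% upper bound goes from 71.2% to 78.1%, past the 75% limit in the Synopsis.
- 7 to 8 of 12: the observed rate goes from 7/12 = 58.3% to 8/12 = 66.7%, past the 60% criterion in Section 8.
- 4 to 5 of 12: the upper bound goes from 55.9% to 63.8%. This applies if the 60% criterion refers to the bound.

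| Lines crossed | r = 50%, p from 0.5% to 5% | r = 30%, p from 0.5% to 5% |
|---|---|---|
| 6 to 7 or 7 to 8 | 1.2% to 11.3% | 0.3% to 3.6% |
| 4 to 5 | 0.5% to 4.5% | 0.9% to 9.7% |

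**What scheduled draws would cover.** For Cohort 2, Section 4.7 states: "The DLT evaluation period will extend from day 1 week 1 to the end of week 6". That is 42 days. Chemistry is drawn at Weeks 1 to 4 and then at Week 7. Nominally, Week 4 day 1 is day 3 × 7 + 1 = 22, and Week 7 day 1 is day 6 × 7 + 1 = 43. With the 72-hour allowance, the Week 7 sample falls on days 40 to 43. The stretch without a sample is therefore days 23–39 (17 days) at best and days 23–42 (20 of 42 days, 48%) at worst.

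**The case against.** The strongest reply is that Appendix 3 says what to do once an event is known and does not set surveillance. Both targeted drugs are approved at the Cohort 2 doses, and the plan leaves extra tests to the treating physician. AST, creatinine and LDH are on the scheduled panel and might prompt a CPK test; creatinine in particular serves the renal-impairment limb. This is fair as far as it goes, and it is why the claim is limited to silent events. But nothing in the plan ties any of those results to a CPK draw, and discretion is a weak safeguard for an event defined by having no symptoms.

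Several points about scale stand:

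- The top of the assumed range sets the silent, missed rate equal to the doublet's whole Grade 3 or 4 figure, and it alone produces the 46% and 97.5%.
- One rate p serves both Grade 4 events (the dose rule) and Grade 3 or higher events (the DLT count).
- The figure for 72 patients requires that the quadruplet be chosen and that the Section 5.2.6 panel apply in Phase II. Section 3.1 cites a Table 5.2.3 that is not in the text.
- The first row of DLT figures combines two lines. At r = 50%, 6 to 7 alone gives 0.7% to 6.9%, and 7 to 8 alone gives 0.5% to 5.2%.

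The remedy is also partial. Beyond the sampling gap, binimetinib is taken at home twice daily and the Week 2 and 3 draws are not infusion visits, so pre-dose review does not by itself stop the next tablet. CPK is not the only such gap: Appendix 3 acts on an asymptomatic fall in LVEF with no echocardiogram row, and Appendix 2 acts on QTcF with EKG marked at screening only. The EKG reading is less secure, since the Imaging row is also marked only at screening, although a footnote requires scans every 12 weeks.

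**Conclusion.** The concern holds. The plan has a mandatory hold, reduce or stop rule for silent Grade 4 CPK and no scheduled CPK measurement, so the rule cannot work reliably for those events. This conclusion rests on the text alone and applies wherever binimetinib is given: Cohort 2, and Phase II if the quadruplet is selected. Cohort 1 is unaffected.

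The size is uncertain because the documents give no applicable rate. The calculated ranges depend on the assumed 0.5% to 5%, and the DLT figures also on independence. They describe shifts in a count, not wrong decisions, since Section 8 has the recommended regimen follow a joint review of all clinical data. No magnitude is claimed for QTcF. The correction is worth making on safety grounds, whatever the true rate.

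**What to change.** Add CPK to the baseline list in Section 5.2.1 and to the serum chemistry panel in Section 5.2.6, at minimum for every patient receiving binimetinib. Run it on blood already drawn: screening, Weeks 1 to 4, the Week 7 pre-dose sample, and later chemistry draws. As an option, mark an EKG at an existing on-treatment visit such as Week 4, so that the QTcF rule in Appendix 2 has a scheduled reading.

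The cost is one extra analyte on six existing draws per patient through Week 7 (screening, Weeks 1, 2, 3, 4 and 7) and on later draws, with no new visit or venipuncture. Some asymptomatic rises will lead to holds that would not otherwise happen, which is what Appendix 3 prescribes, and the observed DLT rate may read slightly higher. Results would have to be back before dosing unless CPK is given the exemption that Section 5.2.6 grants amylase and lipase. The gap between the Week 4 and Week 7 draws would remain.
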